--	--

	
Exclusion criteria:
 
Subjects will be excluded if they meet any of the following criteria:
 
 1. First day of dosing with tesevatinib is less than 2 weeks from the last treatment of cytotoxic chemotherapy, biological therapy, or immunotherapy, and less than 6 weeks for nitrosoureas and mitomycin C. Surgical procedures must have been performed at least 2 weeks prior to the start of study treatment. Subjects must have recovered from the reversible effects of prior lung cancer treatments, including surgery and radiation therapy (excluding alopecia). 2. First day of dosing with tesevatinib is less than 4 weeks from the last radiotherapy of the brain or spinal cord/cauda equina. 3. First day of dosing with tesevatinib is less than 2 weeks from treatment with another investigational agent. 4. Treatment with erlotinib must be discontinued at least 3 days prior to first dose of tesevatinib and treatment with afatinib or other tyrosine kinase inhibitor must be discontinued at least 3 days prior to first dose of tesevatinib. 5. Any concurrent therapy for LM other than the specified treatment in this study. 6. Taking any medication known to moderately or severely inhibit the CYP3A4 isozyme or any drugs that are CYP3A4 inducers (including anti-epileptic agents such as phenytoin). A stable regimen (≥ 4 weeks) of antidepressants of the SSRI class is allowed (common SSRIs include escitalopram oxalate, citalopram, fluvoxamine, paroxetine, sertraline, and fluoxetine). 7. Taking any drugs associated with torsades de pointes or known to moderately or severely prolong the QTc(F) interval. 8. Has evidence of active heart disease such as myocardial infarction within the 3 months prior to study entry; symptomatic coronary insufficiency congestive heart failure; moderate or severe pulmonary dysfunction. 9. History of torsades de pointes, ventricular tachycardia or fibrillation, pathologic sinus bradycardia (< 50 bpm), heart block (excluding first degree block, being PR interval only), or congenital long QT syndrome. Subjects with a history of atrial arrhythmias should be discussed with the medical monitor. 10. Has an active infectious process. 11. Female subject who is pregnant or lactating. 12. Known contraindication to MRI, such as cardiac pacemaker, shrapnel, or ocular foreign body. 13. Has marked prolongation of QTc(F) interval at screening or Cycle 1 Day 1 (QTc[F] interval > 470 msec) using the Fridericia method of correction for heart rate. 14. GI condition that interferes with drug absorption. 15. Non-malignant neurological disease that would interfere with evaluation of symptoms or signs of leptomeningeal metastases. 16. Contraindications to lumbar puncture: 
 a) International normalized ratio (INR) > 1.5 b) Platelets $< 50 \times 10^9/L$ (Note that platelets are required to be $\geq 100 \times 10^9/L$ at

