Prohibited treatments	
 • Other investigational drugs • Concurrent anti-tumor therapies such as chemotherapy, gene therapy, biologics, tyrosine kinases inhibitors, radiation therapy, or other immunotherapy • Medications associated with torsades de pointes or known to moderately or severely prolong the QTc(F) interval, including anti-arrhythmic medications within 2 weeks prior to Day 1 of treatment in the study. • Tesevatinib is largely metabolized by CYP3A4. Therefore, taking any medication known to moderately or severely inhibit the CYP3A4 isozyme or any drugs that are CYP3A4 inducers (including anti-epileptic agents such as phenytoin). A stable regimen (≥ 4 weeks) of antidepressants of the SSRI class is allowed (common SSRIs include escitalopram oxalate, citalopram, fluvoxamine, paroxetine, sertraline, and fluoxetine).

	
 • Steroid medications are allowed • Use of proton pump inhibitors, H2 antagonists, and antacids is allowed, with restrictions • Tesevatinib is a MATE inhibitor. MATE transporter substrates and/or inhibitors should be used with caution

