Efficacy	
For subjects with BM (Cohort A and Cohort C) efficacy will be evaluated by RECIST 1.1 criteria separately for non-CNS tumor lesions and for BMs at screening, at Cycle 2 Day 1 (for BM), at Cycle 3, and then every 2 cycles (approximately 8 weeks) thereafter until disease progression.
 
For subjects with LM (Cohort B), symptoms attributed to leptomeningeal disease will be evaluated at screening, Cycle 1 Day 1, at Cycle 1 Day 14, at Cycle 2 Day 1, at Cycle 3, and then every 2 cycles (approximately 8 weeks) thereafter until disease progression. CTCAE v4.03 (www.hrc.govt.nz/sites/default/files/CTCAE%20manual%20-%20DMCC.pdf) will be utilized for the evaluation of symptoms and signs attributed to leptomeningeal disease. Symptom improvement is defined as a decrease in 1 grade in at least one CTCAE v4.03 symptom or sign attributed to leptomeningeal metastases without worsening of other symptoms or signs that are attributed to leptomeningeal metastases. Symptom progression is defined as an increase of 1 grade in at least one CTCAE v4.03 symptom or the appearance of new symptoms or signs of LM. Symptoms or signs attributed to leptomeningeal metastases will be followed as one component of the efficacy evaluation for Cohort B.
 
In addition to bone scan at screening, scans of the thorax and abdomen will be performed at screening, at Cycle 3, and then every two cycles thereafter until disease progression. Radiological disease assessments by brain MRI will be performed at screening, at Cycle 2 Day 1, at Cycle 3 Day 1, and then every two cycles until disease progression. Response for peripheral disease and for BM will be evaluated according to RECIST, Version 1.1. Response will be recorded separately for non-CNS disease, for BM, and for LM. All CT and MRI scans will be collected for central review. All clinical decisions during the study will be based on local site radiology assessments, which will also be used for the primary efficacy analysis.
 
For subjects with LM (Cohort B), NSCLC cells in the CSF will be evaluated during the study (screening, Day 14 of Cycle 1, and on Day 1 of Cycle 3) for malignant cells both by standard cytological analysis and by a rare cell detection methodology. CSF obtained at the same time points will be evaluated for protein and glucose levels. Response will be based on standard cytological analysis if cytology was positive at screening. Response categories will be complete response (CR) (no malignant cells, which must be present on 2 consecutive CSF evaluations to support response of CR), and non-PR, non-progressive disease (PD) (continued presence of malignant cells). PD will not be defined by CSF cytology.
 
For subjects with LM (Cohort B), CSF for isolation of cell-free DNA will be collected at screening, Day 14 of Cycle 1, and on Day 1 of Cycle 3. Evaluation for EGFR mutations will be performed. Quantitation of EGFR mutations in cell-free DNA will be utilized for an exploratory efficacy analysis.
 
LM will also be evaluated by serial MRI of the brain. For patients with positive findings of LM on MRI at screening, response categories will be CR (no evidence of

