8.6 Inclusion Criteria – Cohort C

Subjects will be included if they meet the following criteria:

1. Age ≥ 18 years old.
2. NSCLC with EGFR mutation (either exon 19 deletion or L858R mutation or an EGFR mutation).
3. No prior systemic treatment for NSCLC. Treatment with systemic steroids is not considered systemic treatment for NSCLC.

-
4. No prior radiation therapy to the CNS (brain or spinal cord)
 5. At least one measurable BM by RECIST 1.1 criteria (≥ 10 mm in longest diameter) in a subject with asymptomatic or minimally symptomatic brain metastases who does not require immediate surgical or radiation therapy in the opinion of the treating investigator and in the opinion of a radiation therapy or neurosurgical consultant.
 6. Subjects in Cohort C may have asymptomatic LM detected by MRI.
 7. ECOG Score ≤ 2 .
 8. No history of another malignancy in the 5 years prior to study entry, except treated non-melanoma skin cancer or superficial bladder cancer or carcinoma-in-situ of the cervix or Stage 1 or 2 cancers of other sites that have been surgically treated and have not recurred.
 9. Adequate organ and bone marrow functions as follows:
 - a. Serum creatinine ≤ 1.5 mg/dL
 - b. Total bilirubin $\leq 1.5 \times$ ULN (except in patients diagnosed with Gilbert's disease where bilirubin must be $\leq 3 \times$ ULN).
 - c. ALT and AST $\leq 3 \times$ ULN
 - d. WBC $> 3000/\text{mm}^3$
 - e. Absolute neutrophil count $\geq 1500/\text{mm}^3$
 - f. Platelet count $> 100,000/\text{mm}^3$
 - g. Hemoglobin > 8 g/dL
 10. Serum potassium and magnesium levels above the LLN.
 11. No coexisting medical problems of sufficient severity to limit compliance with the study.
 12. Willing and able to sign written informed consent and be able to comply with the study protocol for the duration of the study.
 13. Female subjects of childbearing potential have a negative pregnancy test at screening. Females of childbearing potential are defined as sexually mature women without prior hysterectomy or who have had any evidence of menses in the past 12 months. However, women who have been amenorrheic for 12 or more months are still considered to be of childbearing potential if the amenorrhea is possibly due to prior chemotherapy, anti-estrogens, or ovarian suppression.

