14 EFFICACY

In addition to bone scan at screening, CT scans of the thorax and abdomen will be performed at screening, after Cycle 2, and then every two cycles thereafter until disease progression.

Radiological disease assessments by brain MRI will be performed at screening, at C2D1, at C3D1, and then every two cycles until disease progression. Response for peripheral disease and for BM will be evaluated according to RECIST, Version 1.1. Response will be recorded separately for non-CNS disease, for BM, and for LM. All CT and MRI scans will be collected for central review. All clinical decisions during the study will be based on local site radiology assessments, which will also be used for the primary efficacy analysis.

For subjects with BM (Cohort A and Cohort C) efficacy will be evaluated by RECIST 1.1 criteria separately for non-CNS tumor lesions and for BMs at Screening, at Cycle 2 Day 1 (for BM), at Cycle 3, and then every 2 cycles (approximately 8 weeks) thereafter until disease progression.

For subjects with LM (Cohort B), symptoms attributed to leptomeningeal disease will be evaluated at screening, Cycle 1 Day 1, at Cycle 1 Day 14, at Cycle 2 Day 1, at Cycle 3, and then every 2 cycles (approximately 8 weeks) thereafter until disease progression.

The response efficacy endpoints will be evaluated separately for peripheral disease, for BM, and for LM, and a summary response will also be derived (See Table 14-1). For LM, if positive CSF cytology and MRI diagnostic findings were both present at screening, complete response (CR) requires the absence of LM by both modalities. For LM, CR also requires the complete resolution of symptoms and signs attributed to LM. Best overall response, duration of response, and duration of stable disease will be reported, based on the examples in Table 14-1. The median PFS, rate of CNS non-progression at 3 and 6 months, non-CNS time to progression, CNS TTP, and median OS also will be assessed.

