- Diagnosis of BM CR or PR, or LM CR, requires that steroids be at or lower than dose of steroids at Cycle 1 Day 1 (if subject is receiving steroids)
- All summary response examples assume that no new lesions are present. A new peripheral tumor or brain metastasis, or symptom progression of LM will lead to a summary response of PD in that category.

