14.2 Cohort B – Leptomeningeal Metastases

For subjects with LM, symptoms attributed to leptomeningeal metastases will be evaluated at screening, Cycle 1 Day 1, Cycle 1 Day 14, Cycle 2 Day 1, Cycle 3 Day 1, and then every 2 cycles (approximately 8 weeks) thereafter until disease progression, as well as at the End of Drug Treatment visit. CTCAE v4.03

(www.hrc.govt.nz/sites/default/files/CTCAE%20manual%20-%20DMCC.pdf) will be utilized for the evaluation of symptoms and signs attributed to leptomeningeal metastases. Symptom improvement is defined as a decrease in 1 grade in at least one CTCAE v4.03 symptom or sign attributed to leptomeningeal metastases without worsening of other neurologic symptoms or signs attributed to leptomeningeal metastases. Symptom progression is defined as an increase of 1 grade in at least one CTCAE v4.03 symptom attributed to leptomeningeal metastases or the appearance of new symptoms or signs of LM. Symptoms or signs attributed to leptomeningeal metastases will be followed as one component of the efficacy evaluation for Cohort B.

For subjects with LM, NSCLC cells in the CSF will be evaluated during the study (screening, Day 14 of Cycle 1, and on Day 1 of Cycle 3) for malignant cells both by standard cytological analysis and by a rare cell detection methodology. CSF obtained at the same time points will be evaluated for protein and glucose levels. Response will be based on standard cytological analysis if cytology was positive at screening. Response categories will be CR (no malignant cells, which must be present on 2 consecutive CSF evaluations to support response of CR), and non-PR, non-PD (continued presence of malignant cells). PD will not be defined by CSF cytology.

For subjects with LM (Cohort B), CSF for isolation of cell-free DNA will be collected at screening, Day 14 of Cycle 1, and Day 1 of Cycle 3. Evaluation for EGFR mutations will be performed. Quantitation of EGFR mutations in cell-free DNA will be utilized for an exploratory efficacy analysis.

LM will also be evaluated by serial MRI of the brain. For patients with positive findings of LM on MRI at screening, response categories will be CR (no evidence of LM on MRI), or non-PR, non-PD (continued presence of evidence of LM on MRI). PD for LM will not be defined by MRI.

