# 1.3 Efficacy Assessments

## 1.3.1 Efficacy Endpoints

## 1.3.1.1 Primary endpoints

Cohorts A and C: efficacy (changes in BM size) will be evaluated by RECIST 1.1 criteria separately for non-CNS tumor lesions and for BMs at screening, at Cycle 2 Day 1 (for BM), at Cycle 3 Day 1, and then every 2 cycles (approximately 8 weeks) thereafter until disease progression.

For Cohort B: symptoms and signs attributed to leptomeningeal disease will be evaluated at screening, Cycle 1 Day 1, at Cycle 1 Day 14, at Cycle 2 Day 1, at Cycle 3, and then every 2 cycles (approximately 8 weeks) thereafter until disease progression National Cancer Institute CTCAE (NCI CTCAE; Version 5). Symptom improvement is defined as a decrease in 1 grade in at least one CTCAE v4.03 symptom or sign attributed to LM without worsening of other symptoms or signs that are attributed to LM. Symptom progression is defined as an increase of 1 grade in at least one CTCAE v4.03 symptom or the appearance of new symptoms or signs of LM.

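### Cohort B's primary endpoint counts a one-grade symptom fall with no steroid condition, although the protocol sets one for brain and leptomeningeal response

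*Protocol*

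**What the plan says.** Improvement in CTCAE symptoms and signs is Cohort B's primary objective (Protocol 6; SAP 1.1.2) and the basis of its sample size (Protocol 16.2; SAP 1.2.1). It is defined in three places:

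- Protocol synopsis, Efficacy: "Symptom improvement is defined as a decrease in 1 grade in at least one CTCAE v4.03 symptom or sign attributed to leptomeningeal metastases", provided other LM-attributed symptoms and signs have not worsened.
- Protocol 14.2: "a decrease in 1 grade in at least one CTCAE v4.03 symptom or sign attributed to leptomeningeal metastases without worsening of other neurologic symptoms", with LM-attributed signs treated in the same way.
- SAP 1.3.1.1: the same one-grade fall, "without worsening of other symptoms or signs that are attributed to LM".

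None of the three refers to steroids, and the SAP does not mention them anywhere.

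Footnote 2 to Table 14-1 (Protocol 14) takes a different line for the other responses. It names complete response (CR) or partial response (PR) of brain metastases, then continues "or LM CR, requires that steroids be at or lower than dose of steroids at Cycle 1 Day 1 (if subject is receiving steroids". Section 14 also ties LM CR to symptoms: "For LM, CR also requires the complete resolution of symptoms and signs attributed to LM".

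On use during the study, the synopsis list of prohibited treatments states "Steroid medications are allowed". Section 12 says the same. Neither sets a dose limit or a stability period. Section 11.1.3.2 includes a short oral steroid course among its suggestions for Grade 3 rash. The study is open-label and nonrandomized (Protocol 7.3).

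**The concern.** The protocol already accepts that a change in steroid dose can make a response hard to attribute to the drug, which is why footnote 2 exists. Because LM CR requires the symptoms to resolve fully, those symptoms are judged under the steroid condition when they contribute to LM CR. A one-grade fall in the same symptoms, which is easier to reach and is the primary endpoint, is judged without it. The primary brain-metastasis response in Cohorts A and C has the protection; the primary endpoint in Cohort B does not.

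The definition asks for no confirmation and no minimum duration, and symptoms are graded from Cycle 1 Day 14 onward. One visit after a steroid start or increase could therefore qualify a subject. With no comparator, the observed rate cannot separate relief due to steroids from relief due to tesevatinib.

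**Working it through.** **1. Which outcomes carry a steroid condition**

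| Outcome | Role | Steroid condition |
|---|---|---|
| Brain-metastasis CR or PR | Primary, Cohorts A and C | Yes (Table 14-1, footnote 2) |
| LM CR, including full symptom resolution | LM response category | Yes (Table 14-1, footnote 2) |
| One-grade LM symptom improvement | Primary, Cohort B | None (synopsis, 14.2, SAP 1.3.1.1) |

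**2. Whether another rule fills the gap**

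- SAP 1.2.5 makes a non-evaluable response a non-response. A subject on added steroids with a recorded grade fall is evaluable, so this does not apply.
- Protocol 12.1 asks for medical monitor approval of additional treatment. It does not say how the subject is then counted.
- SAP Table 2 lists concomitant medications. A listing is not an endpoint rule.

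**3. How far the progression rule narrows the route**

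A one-grade rise in an LM symptom, or a new LM symptom or sign, is symptom progression (14.2) and gives progressive disease in that category (Table 14-1, footnote 3). Symptoms are followed until progression. A subject given steroids because graded LM symptoms worsened should therefore often have progressed already. Three cases remain open:

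- steroids added while LM symptoms are stable;
- steroids added for another reason, such as brain metastases (allowed in Cohort B by inclusion criterion 7) or rash;
- steroids added for worsening between visits. After Cycle 3, symptom assessments are about 8 weeks apart, and the unscheduled-visit list in 9.2.13 does not include LM symptom assessment.

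**4. The plan's own figures**

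Inputs are N = 20 and a 20% improvement rate (SAP 1.2.1).

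- P(at least 2) = 1 − [0.8^20 + 20(0.2)(0.8^19)] = 1 − [0.0115 + 0.0576] = 0.931. The plan says over 90%.
- P(at least 3) = 0.9308 − 190(0.2²)(0.8^18) = 0.9308 − 0.1369 = 0.794. The plan says approximately 80%.

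Both reproduce. They depend only on the rate of subjects counted as improved, whatever caused the improvement.

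**5. Size per affected subject**

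One subject is 1/20 = 5 percentage points. The documents give no rate of steroid starts or of steroid-driven relief. The counts below are therefore assumptions: 4 of 20 counted as improved, of whom k improved only on added steroids. Intervals are exact (Clopper-Pearson): lower limit Beta(0.025; x, 21 − x), upper limit Beta(0.975; x + 1, 20 − x).

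| k | x/20 with the condition | Rate | Exact 95% CI |
|---|---|---|---|
| 0 | 4/20 | 20% | 5.7–43.7% |
| 1 | 3/20 | 15% | 3.2–37.9% |
| 2 | 2/20 | 10% | 1.2–31.7% |

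The error can also run the other way. A true drug responder who is on added steroids at every qualifying visit would be removed by the condition, which lowers the rate by the same 5 points.

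**6. The symptom baseline**

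LM symptoms are graded at screening and again at Cycle 1 Day 1, and no passage says which visit the grade fall is measured from. Footnote 2 measures steroid dose from Cycle 1 Day 1. If the fall were taken from screening, relief from steroids started between the two visits would satisfy a Day 1 dose condition and still count as improvement.

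**The case against.** The strongest reply is the progression rule in step 3, together with the requirement that no other LM symptom worsen. It removes much of the most obvious scenario, steroids given for worsening LM symptoms. That part stands and limits the concern to the three open cases.

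A second reply is that conditioning can penalise real responders. Acneiform rash is an expected effect of the drug (Protocol 5.2.1), and systemic steroids are among the suggestions for Grade 3 rash. That also stands, and it is why both rates should be shown.

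Third, symptoms are described as one component of Cohort B efficacy; CSF and MRI clearing are also reported, and LM CR has its own steroid condition. This helps a reader weigh the evidence, but it does not change the primary rate.

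Two stronger readings are tempting and are not supported:

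- A reader might infer that Cohort B exclusion 5, "Any concurrent therapy for LM other than the specified treatment in this study", conflicts with the permission for steroids, especially as only Cohort C is told "Treatment with systemic steroids is not considered systemic treatment for NSCLC". Footnote 2 already provides for subjects receiving steroids at Cycle 1 Day 1, and the prohibited-treatment lists name anti-tumor therapies while separately allowing steroids. Read together, these passages permit steroids. The Cohort C sentence concerns prior treatment for eligibility. Neither text bears on how improvement is counted.
- A reader might treat the chance of reaching 3 improvements without drug activity as a false-positive rate. At an assumed 10% steroid-driven improvement and no drug effect, that chance is 32.3%. But SAP 2 plans no formal test, and no decision is tied to 3 responders, so it is not an error rate.

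**Conclusion.** The gap is real and should be fixed. As written, the plan counts a one-grade LM symptom fall after a systemic steroid start or increase as improvement, and nothing in either document says otherwise. The resulting rate and its interval can overstate tesevatinib activity in a cohort with no control arm.

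The size cannot be derived from the documents. What is certain is 5 points per affected subject at n=20; the table above rests on assumed counts of 0 to 2. The documents do not support saying that the rate will be inflated, only that it can be and that the plan could not show whether it was. The harm is an estimate that is hard to interpret. The sample-size arithmetic is correct and is not in question.

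**What to change.** In the synopsis, Protocol 14.2 and SAP 1.3.1.1:

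1. Extend the footnote 2 condition to symptom improvement. Count improvement only at a visit where the systemic corticosteroid dose is at or below the Cycle 1 Day 1 dose. State that a new start after Cycle 1 Day 1 is an increase, because the footnote's closing qualifier leaves that case unclear. State that topical steroids do not count, so that rash creams do not disqualify a visit. A subject can still qualify at any other visit that meets the condition.
2. Measure the grade fall from the same Cycle 1 Day 1 visit. Relief from steroids started between screening and Day 1 is then less likely to count. Steroids started just before Day 1 may still act afterwards, so this reduces the problem but does not remove it.
3. Report the rate with and without the condition, each with its exact 95% interval. The difference is the subjects whose qualifying visits were all on a raised dose, so a true responder on added steroids remains visible.

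Also confirm that the eCRF captures steroid dose and dates. The synopsis section on concomitant medications asks for drug, reason and duration, and for changes asks for type, duration and indication. It does not name dose, which footnote 2 already needs.

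The cost is a wording change in both documents, one additional rate, and possibly one eCRF field. The conditioned rate may be lower, and some true responders may be counted as not improved under it. This is a counting rule only and leaves steroid care unchanged.

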8.4 Inclusion Criteria – Cohort B

A subject must meet the following criteria to be eligible for entry into the study:

1. Age \geq 18 years old.
2. History of NSCLC with EGFR mutation (either exon 19 deletion or L858R mutation or of an EGFR mutation that has had a clinical response to erlotinib, afatinib, or gefitinib in the patient being enrolled).
3. Presentation with LM at initial presentation with no prior systemic treatment, or occurrence or progression of LM while receiving first line therapy (either erlotinib or afatinib or gefitinib) for at least 14 days. Patients may have received osimertinib (or other agents inhibiting the T790M EGFR mutation) as second line therapy. If LM progression occurs after osimertinib, patient will be eligible.
4. Presence of at least one CTCAE 4.03 symptom or sign of at least Grade 1 attributed to leptomeningeal metastases.
5. Diagnosis of LM by:
 - a) Cytological evidence in CSF sample of LM due to NSCLC, and/or
 - b) Findings on gadolinium-enhanced MRI
6. No clinically significant progression outside of the CNS on most recent EGFR inhibitor therapy.
7. Concomitant brain metastases and brain metastases previously treated with radiation therapy are allowed. (Subjects with symptoms or signs attributed to LM will be enrolled in Cohort B whether or not they have brain metastases.)

-
8. ECOG Score ≤ 2 .
 9. No history of another malignancy in the 5 years prior to study entry, except treated non-melanoma skin cancer or superficial bladder cancer or carcinoma-in-situ of the cervix or Stage 1 or 2 cancers of other sites that have been treated surgically and have not recurred.
 10. Adequate organ and bone marrow functions as follows:
 - a) Serum creatinine ≤ 1.5 mg/dL
 - b) Total bilirubin $\leq 1.5 \times$ ULN (except in patients diagnosed with Gilbert's disease where bilirubin must be $\leq 3 \times$ ULN).
 - c) ALT and AST $\leq 3 \times$ ULN
 - d) WBC $> 3000/\text{mm}^3$
 - e) Absolute neutrophil count $\geq 1500/\text{mm}^3$
 - f) Platelet count $> 100,000/\text{mm}^3$
 - g) Hemoglobin > 8 g/dL
 11. Serum potassium and magnesium levels above the LLN.
 12. No coexisting medical problems of sufficient severity to limit compliance with the study.
 13. Willing and able to sign written informed consent and be able to comply with the study protocol for the duration of the study.

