9.1.13 Tumor Assessments

In addition to bone scan at screening, CT scans of the thorax and abdomen will be performed at screening, after Cycle 2, and then every two cycles thereafter until disease progression.

Radiological disease assessments by brain MRI will be performed at screening, at Cycle 2 Day 1, at Cycle 3 Day 1, and after every two cycles until disease progression. Response for peripheral disease and for BM will be evaluated according to RECIST, Version 1.1. Response will be recorded separately for non-CNS disease, for BM, and for LM. All CT and MRI scans will be collected for central review. All clinical decisions during the study will be based on local site radiology assessments, which will also be used for the primary efficacy analysis.

For subjects in cohort B, symptoms or signs attributed to leptomeningeal metastases will be followed. Symptoms attributed to leptomeningeal metastases will be evaluated at screening, at Cycle 1 Day 1; at Cycle 1, Day 14; at Cycle 2 Day 1, at Cycle 3 Day 1, and then every 2 cycles (approximately 8 weeks) thereafter until disease progression, as well as at the End of Drug Treatment visit.

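### Cohort B: a grade rise in an existing leptomeningeal sign is not, on the literal text, a progression event, so CNS TTP, CNS non-progression and, less so, PFS can only read the same or longer

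*Protocol*

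**What the plan says.** Protocol Section 14.2 defines improvement first: "Symptom improvement is defined as a decrease in 1 grade in at least one CTCAE v4.03 symptom or sign attributed to leptomeningeal metastases", provided it occurs "without worsening of other neurologic symptoms or signs attributed to leptomeningeal metastases". The next sentence defines progression: "Symptom progression is defined as an increase of 1 grade in at least one CTCAE v4.03 symptom attributed to leptomeningeal metastases or the". Its second limb, which closes that sentence, is "appearance of new symptoms or signs of LM".

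The synopsis has "Symptom progression is defined as an increase of 1 grade in at least one CTCAE v4.03 symptom or the appearance of new symptoms or" and SAP 1.3.1.1 has "Symptom progression is defined as an increase of 1 grade in at least one CTCAE v4.03 symptom or the appearance of new symptoms"; in both, new signs are named next. All three places give improvement on a symptom or sign, and all three give the worsening limb of progression on a symptom only. The synopsis and SAP also leave out the attribution to LM in that limb, which Section 14.2 includes.

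Section 14.2 rules out CSF cytology and MRI as ways to define LM progression. Note 3 to Table 14-1 makes symptom progression the route to PD in the LM category. Section 8.4, criterion 4, admits a subject on "Presence of at least one CTCAE 4.03 symptom or sign of at least Grade 1 attributed to leptomeningeal metastases", so a sign alone is enough for entry.

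PFS, CNS TTP and CNS non-progression at 3 and 6 months are secondary endpoints (SAP 1.3.1.2). The SAP gives no event definition of its own for them.

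**The concern.** A subject may have an LM sign at entry that later rises by a grade, with no symptom worse and nothing new. The worsening limb names only a symptom, and the other limb needs a new finding, so this change meets neither. With cytology and MRI excluded, nothing else records LM progression at that point.

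The error runs one way. Leaving out one kind of event can delay or remove a first event but cannot bring one forward. Cohort B is a single open-label group, so no control arm carries the same error. If investigators instead take *symptom* to cover signs, the event would depend on the reader, across about 10 sites in the United States and up to 6 in South Korea and Taiwan (Section 7.1).

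**Working it through.** **The plan's own figure.** Cohort B has N = 20 and an assumed improvement rate of 20%. The binomial terms are:
- P(0) = 0.8^20 = 0.0115
- P(1) = 20 × 0.2 × 0.8^19 = 0.0576
- P(2) = 190 × 0.04 × 0.8^18 = 0.1369

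So P(at least 2) = 1 − 0.0692 = 0.931 and P(at least 3) = 1 − 0.2061 = 0.794. Both agree with the plan (over 90%, approximately 80%). They rest on improvement, so the progression wording does not touch them.

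**What happens to an existing LM sign, rule by rule.**

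| Rule | Does an existing sign count? |
|---|---|
| Improvement (synopsis, 14.2, SAP 1.3.1.1) | Yes, a one-grade fall counts |
| Block on improvement (same places) | Yes, worsening of another sign cancels it |
| LM complete response (Section 14) | Yes, signs must resolve |
| Progression, worsening limb (same three places) | Not named |
| Progression, new-finding limb | Only if the sign is new |

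**Is the gap closed elsewhere?** Section 11.1.1 refers CNS progression to Appendices A and B, but A is headed for non-CNS response and B is the ECOG scale. The borderline-progression rule in Section 14 speaks of worsening CNS symptoms. Neither adds signs.

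**Size (illustration only).** Let f be the share of first CNS events that are worsening of an existing sign alone. The documents give no value; 10% to 30% is assumed, with exponential event times.

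*Ceiling: missed events are ignored and the hazard of other events is unchanged.* The observed hazard is (1 − f) times the true one, so the median is multiplied by 1/(1 − f). A true landmark rate S reads S^(1−f).

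| f | Median multiplied by | True 50% non-progression reads |
|---|---|---|
| 10% | 1.11 | 53.6% |
| 20% | 1.25 | 57.4% |
| 30% | 1.43 | 61.6% |

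*Each miss is caught 8 weeks later by another event.* Take a true median of 13 weeks, so λ = ln 2 / 13 = 0.0533. Beyond week 8, survival is e^(−λt) × [1 + f(e^(8λ) − 1)], with e^(8λ) = 2^(8/13) = 1.532. The observed median is 13 + ln(1 + 0.532f)/λ:
- f = 10%: 13.97 weeks (7.5% longer)
- f = 20%: 14.90 weeks (14.6% longer)
- f = 30%: 15.78 weeks (21.4% longer)

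**The case against.** The best answer is that the protocol uses *symptom* as an umbrella word. Symptom improvement is itself defined to include signs. Section 16.3.6 describes the symptom-or-sign endpoint as improvement in symptoms, and Table 4-2 labels the whole assessment as LM symptoms. On that reading a worsening sign already counts. This stands in part: the loose reading is possible. It is not secure, because the progression sentence names symptoms and signs separately in its second limb, and Section 15.2 also separates the two terms. What remains is either a gap or an ambiguity, and the same edit cures both.

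The documents do not support four stronger readings that a reader might reach:

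- **A worsening cranial nerve palsy as the plain example.** The study rationale (synopsis and Section 5.3.1) lists cranial neuropathies among neurologic symptoms, so that case could count as the text stands.
- **Worsening signs never count against the drug.** Worsening of another LM sign cancels improvement, the Cohort B primary endpoint, and signs must resolve for LM complete response. The gap is confined to the progression endpoints.
- **The 11% to 43% as an expected bias.** It needs an assumed share applied to all first CNS events, with no later catch. Section 8.4 allows concomitant brain metastases, whose progression is also a CNS event. If 30% of CNS events were of that kind (assumed), a 10% to 30% share of LM worsenings alone would be f = 7% to 21%, and the ceiling about 8% to 27%.
- **The SAP drops the End of Treatment grading.** Its visit list does not mention that visit, but Section 9.1.13 requires the assessment "as well as at the End of Drug Treatment visit". So do Sections 9.2.10 and 14.2 and Table 4-2, and nothing in the SAP excludes those data.

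**Conclusion.** The point holds as a defect in the event definition for secondary endpoints. All three statements of the rule leave worsening of an existing sign out of progression, and no other passage puts it back. Where such worsening is the first event, CNS TTP and 3- and 6-month CNS non-progression can only read the same or longer. PFS is affected less, because peripheral progression and death also end it. The direction follows from the definition; the size does not.

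With f assumed at 10% to 30%, inflation of the median CNS TTP is at most about 11% to 43%. That is a ceiling as long as a subject whose sign has worsened is at no lower risk of other events than before. With an 8-week catch and a 13-week median it is about 7.5% to 21%. If sites already count worsening signs as symptoms, it is smaller still and varies by site. The SAP plans no hypothesis test, so what is at stake is the accuracy of descriptive estimates.

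**What to change.** For the analysis event definition in the synopsis, Section 14.2 and SAP 1.3.1.1, replace *symptom* in the worsening limb with *symptom or sign*, attributed to leptomeningeal metastases, as the improvement rule has it. This also restores the attribution missing from the synopsis and SAP. State in the SAP that this is the LM event for CNS TTP, CNS non-progression and PFS.

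Progression also bears on how long treatment continues (Section 11.1.1). The sponsor should reconcile those passages in the same edit; nothing is proposed here on treatment.

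The cost is a protocol modification under Section 19 and a SAP edit. No new data are needed: signs are already graded by CTCAE under Section 14.2, and SAP Listing 1.1.1 already covers symptoms and signs by visit. The affected estimates stay the same or become shorter. Reporting how many first events are sign-only worsening would replace the assumed f with an observed one.
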